3.5.3 Potential Benefits

The research question in the Primary Objective will directly benefit study participants by identifying women with abnormal cervical cancer screening results and offering treatment to prevent progression to cancer. Previously, women who screened positive for precancerous lesions were referred for care, some of whom are lost to follow-up in navigating the referral process. In enrolling in the study, all eligible women will access immediate treatment in the clinic instead of referral. During screening, some women with potential early-stage cancer may be identified and will be referred for appropriate evaluation and treatment to a gynecologist oncologist at the referral site. Study staff will support these participants through the referral process to ensure they are seen by a Gynecologist Oncologist. The research questions in the Secondary Objectives will not directly benefit individual patients but will contribute to the knowledge of safety and acceptability of this method of treatment for precancerous lesions that may enable widespread adoption of this technique if proved safe and effective. The Exploratory Objective will evaluate provider acceptability of Thermocoagulation thereby providing crucial insights into potential limitations for widespread provider acceptability of this treatment method. All participants may also gain knowledge about cervical cancer screening and prevention from spending more time with study staff and study clinicians. According to KEMRI regulations, participants will only be reimbursed for their transportation expenses related to participation in the study. Hence, for study-specific visits, women will be reimbursed a rate set by KEMRI. Women participating in the study during a scheduled visit will be reimbursed a meal voucher only.

4 Participant Eligibility, Recruitment, and Enrollment

4.1 Eligibility Criteria

4.1.1 Inclusion Criteria

1. Age 30-65 years.
2. Enrolled in HIV care at FACES-supported clinics in Kisumu County.
3. Able to understand a written informed consent document, and willing to sign it.
4. Speaks a language that the consent form and data collection instruments are written in.

4.1.2 Exclusion Criteria

1. Has a history of cervical cancer.
2. Has received any treatment for cervical precancer after screening positive for precancer.
3. Has evidence of cervical infection.
4. Pregnant women are excluded from this study.

4.2 Recruitment and Enrollment

Women receiving care at FACES-supported HIV- clinics will be considered for recruitment into the study. At these clinics, patients are introduced to cervical cancer screening as part of an HIV education session when they enroll in care. Information about cervical cancer and the opportunity for screening is reinforced as part of a general daily health talk given while patients are waiting to be seen for their routine HIV care, and then reinforced through individualized counseling during their clinical visit. Women willing to undergo cervical cancer screening will be screened consecutively for their study eligibility and asked about their willingness to participate in the study.

Screening and informed consent for participation in the study will take place in a private gynecologic exam room prior to a pelvic exam. Women who previously screened positive for HPV (within the last 3 months) but have not undergone treatment will also be eligible for recruitment. Those who screen positive and are eligible for thermal ablation will be offered treatment and will form the study group

Participant Registration

A written, signed, informed consent form (ICF) must be obtained before any study-specific assessments are initiated. A copy of the signed ICF will be given to the subject and a copy will be filed in the medical record. The original will be kept on file with the study records.

All participants consented to the study will be registered in OnCore®, the UCSF Helen Diller Family Comprehensive Cancer Center Clinical Trial Management System (CTMS). The system is password protected.

5 Study Procedures and Assessments

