3.1 Characteristics

We will prospectively enroll four hundred HIV-positive women to undergo cervical cancer screening at FACES-supported MOH clinics in Kisumu County. After informed consent, clinical and demographic information will be collected, and participants will undergo cervical cancer screening using HPV testing. Women who previously screened positive for HPV (within the last 3 months) but have not undergone treatment will also be eligible for recruitment. Women with a positive HPV test will be evaluated for treatment with thermal coagulation, per WHO standards of ablative treatment. Per the WHO and Kenya Ministry of Health guidelines, women who will be candidates for thermal coagulation if the squamocolumnar junction is fully visualized, the cervical lesion covers less than 75% of the cervix, and there is no endocervical component or suspicion of cancer.⁸ Women who are not candidates for ablation will be referred to nearby a referral facility. All participants with a positive HPV test will undergo directed biopsy just prior to treatment for disease ascertainment but proceed to have same-day treatment, according to the WHO guidelines for screen & treat.

At 12-months after treatment, all participants treated at baseline will undergo repeat colposcopy, directed biopsy for those with cervical abnormalities or those with CIN2/3 at baseline, as well as provider collected HPV testing for persistence. Twenty-five percent of women with normal colposcopy will have a random biopsy at 6 or 12-O'Clock to confirm the absence of disease. Pain will be assessed immediately following treatment using a visual analog scale (VAS). The presence and severity of AEs will be assessed 4-6 weeks following treatment via a phone call, or in person visit, if warranted. Healthcare providers offering thermal ablation for the treatment of precancerous lesions will be surveyed at 4-6 week follow-up to evaluate provider acceptability and satisfaction with this treatment method.

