3.3 Sample Size and Power Calculation

The study sample size is calculated based on the primary objective.

We seek to enroll 400 participants in order to obtain sufficient numbers of women who have CIN2/3, our outcome of interest. Based on prior studies in this population, we anticipate approximately 35% of HPV-positive women (N ~ 140) will have biopsy-proven CIN2/3.²⁴ The study design is a non-inferiority trial using results from the only study using standard cryotherapy in a similar population¹⁹ to establish the non-inferiority boundary. We

will compare the efficacy rate in our study using thermocoagulation to the non-inferiority boundary established using the efficacy rate and lower 95% confidence bound from this cryotherapy treatment publication from a similar population.¹⁹

The efficacy results of cryotherapy in the De Vuyst paper were 77.2% (95% CI: 66.4-85.9%).¹⁹ Using 77.2% with a non-inferiority margin of 10% which is at the limit of the confidence bound and is closest to the null effect.²⁴ Using this margin, the new treatment method is hypothesized to be at least as good as cryotherapy. Based on this non-inferiority margin, a sample size of 140 women with CIN2/3 achieves 90% power in using a one-sided test with a significance level of 0.025. Based on this sample size, power of 90%, and significance of 0.025, the minimal detectable effect size (the actual difference between cryotherapy and thermocoagulation) is 0.0102.

We will leverage the robust HIV-care infrastructure at FACES in which patients are seen at every one to three months, and the presence of an established patient tracing system (including home visits) to reduce loss-to-follow-up. Assuming a 14% loss to follow-up, which would result in a sample size of 120, we are still be powered for our non-inferiority margin of 10% with a minimal detectable effect size of 0.0184, with 80% power and an alpha of 0.025. Sample size and non-inferiority calculations used NCSS PASS software and G-Power software.

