3.5 Risks and Benefits

3.5.1 Potential Risks

We anticipate that the potential risks to participants in the study will be minimal. Study subjects may feel discomfort or embarrassment during the pelvic exam. There may be minimal discomfort during self-collection of HPV specimens. Participants may be at risk for psychological or emotional discomfort at different stages of the study if they have a diagnosis of CIN2/3 and learn about the potential risk of cervical cancer. Participants may risk some discomfort and mild spotting after the colposcopy and biopsy. We anticipate that this will be minimal, as exams will be performed by trained clinicians, and thermal coagulation would ablate the biopsied area with the tissue desiccation, hence stopping any bleeding. Other mechanisms to achieve hemostasis at bleeding sites including use of Silver Nitrate sticks will be available to study clinicians. Women who are not eligible for thermocoagulation due to large lesions will be referred to a nearby tertiary facility for further care, per clinic protocol. Following treatment for abnormal screening, women will have vaginal discharge for a few days for which they will be provided anticipatory guidance. During the 12-month follow-up visit, all treated women will have repeat screening with colposcopy and biopsy as needed, as well as repeat HPV-testing with provider collection. Twenty-five percent of women who have normal colposcopy results will have a random biopsy for ascertainment of cure after treatment. This may not have been performed in a routine clinical visit and may be associated with slight discomfort, but the risk to the patient will

be minimized by adequate training of clinicians, and anticipatory guidance provided to the patient. We believe that the benefit of reducing verification bias in performing these biopsies will strengthen the study results and prove a strong case for implementing this treatment method on a large scale.

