We will use the CareHPV™ system which tests for DNA of 14 high risk HPV types (16, 18, 31, 33, 35, 39, 45, 51, 52, 56, 58, 59, 66 and 68).²⁵ The self-collected samples will be placed in a cool area within the FACES laboratory and tests will be run in batches of 90, per the manufacturer's instructions, by a trained laboratory technician. Women who screen positive for HR-HPV will be offered a pelvic exam and treatment per the WHO recommendation.⁴ Visual inspection with acetic acid will be performed at the time of the pelvic exam to determine eligibility for thermal ablation based on the size of the lesion and other characteristics, as recommended by the WHO and Ministry of Health.⁴ A HPV-positive woman will be considered a candidate for thermal coagulation if the squamocolumnar junction is fully visualized, the cervical lesions takes up less than 75% of the cervix, there is no endocervical component of the lesion, and the lesion is not suspicious for cancer. Women who do not meet these criteria will be referred to a tertiary facility for appropriate care.

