7.1 Primary Objective

To evaluate the efficacy of thermal coagulation for the treatment of HIV-positive, HPV-positive women by assessing rates of HPV persistence and CIN2/3 at 12 months after treatment

Four hundred HIV-positive women with positive HPV testing will undergo colposcopy-directed biopsy for disease ascertainment prior to same-day treatment with thermal coagulation. At 12-months after treatment, all participants will undergo repeat HPV testing for persistence, and those who are HPV-positive will undergo repeat colposcopy, and biopsy as indicated for abnormal results, or random biopsy for 25% of those with normal colposcopy. We will define cure as a normal biopsy result or normal colposcopy among those who do not receive a biopsy.

Statistical Analysis: We will report the proportion of women with no evidence of cervical dysplasia at 12-months (primary outcome) follow-up, including 95% confidence intervals. We will extrapolate the rate of disease among those with normal colposcopy based on the rate of disease among the 25% in this group who will receive biopsy, and this will be incorporated in calculating persistence. We will perform a logistic regression to examine predictors of treatment success, using clinical and demographic variables as predictor variables. We will also report the rate of persistence of HPV at follow-up and compare with rates reported in the literature in this same population. We will compare efficacy rates for clearance of CIN2/3 to historical results following cryotherapy treatment in similar settings. A one-sample exact test will be used to compare the obtained efficacy proportion to that of historical controls.

We will leverage the robust infrastructure of the FACES in which patients are seen every one-to three months, and there is an established patient tracing system (including home visits) to reduce loss-to-follow-up. With a loss-to-follow-up rate of 10%, we will still be powered to answer this objective. Prior studies at this clinic have been able to achieve > 90% follow-up rate.³⁶ While limited by the lack of randomization to cryotherapy versus thermocoagulation, this study will provide pilot results that may enable a future randomized study evaluation of these two treatment methods.

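### Section 3.3 counts 140 women with CIN2/3 from 400 HPV-positive women and makes no allowance for those referred away as unsuitable for ablation

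*Combined protocol and SAP*

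**What the plan says.** Section 3.3 states the aim as "We seek to enroll 400 participants in order to obtain sufficient numbers of women who have CIN2/3" and gives the expected yield: "we anticipate approximately 35% of HPV-positive women (N ~ 140) will have biopsy-proven CIN2/3". The synopsis repeats this. The only reduction section 3.3 then makes is a 14% loss to follow-up, which brings the number to 120. The efficacy comparison is built on these figures: "Using 77.2% with a non-inferiority margin of 10" percent, with a one-sided significance level of 0.025.

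The treated cohort is defined elsewhere. Sections 3.1, 5.1 and 5.3 require a fully visible squamocolumnar junction, a lesion covering less than 75% of the cervix, no endocervical component and no suspicion of cancer. Section 5.1 continues: "Women who do not meet these criteria will be referred to a tertiary facility for appropriate care". Section 4.2 says of the women who pass: "Those who screen positive and are eligible for thermal ablation will be offered treatment and will form the study group". Section 3.5.1 anticipates that some will not pass: "Women who are not eligible for thermocoagulation due to large lesions will be referred to a nearby tertiary facility for further care, per clinic protocol".

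Follow-up is limited to treated women. Section 3.1 says "At 12-months after treatment, all participants treated at baseline will undergo repeat colposcopy", and section 5.8 agrees. Section 7.1, however, is worded as if every HPV-positive woman is treated: "Four hundred HIV-positive women with positive HPV testing will undergo colposcopy-directed biopsy for disease ascertainment prior to same-day treatment with thermal coagulation".

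**The concern.** The 35% and the efficacy analysis have different denominators. Section 3.3 states the 35% for HPV-positive women, whereas the analysis can use only women who were HPV-positive, passed the ablation criteria, were treated and returned at 12 months. A woman with CIN2/3 who is referred elsewhere counts towards the 140 but cannot contribute to the efficacy proportion. The plan allows for women lost after treatment and not for women who never receive it.

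At stake is the number on which section 3.3 rests its power statement. The fallback of 120 is obtained from the full 140, so it holds no reserve for ineligible women. This is separate from whether the 400 are counted before or after HPV testing, a question that the wording of section 3.1 raises. The gap described here remains when all 400 are taken to be HPV-positive.

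**Working it through.** **Inputs from the documents.** 400 women and 35% CIN2/3 among HPV-positive women (3.3 and synopsis); 14% loss (3.3); historical cryotherapy rate 77.2% and margin 10 points, so a boundary of 67.2% (3.3); one-sided 0.025 (3.3); a difference of 0.0184 for the 120-woman scenario (3.3), so an assumed true rate of 0.772 + 0.0184 = 0.7904; one-sample exact test (7.1).

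**Input not in the documents.** e, the share of women with CIN2/3 who fail the ablation criteria. I assume 5% to 30% to show the effect. No passage supports a particular value.

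**Step 1: reproduce the plan.** 400 × 0.35 = 140, and 140 × 0.86 = 120.4, stated as 120. Both figures reproduce, with e = 0.

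**Step 2: the 400 are HPV-positive women.** Treated women with CIN2/3 = 400 × 0.35 × (1 − e). After loss, multiply by 0.86. HPV-positive women needed to keep 140 treated with CIN2/3 = 400 / (1 − e), rounded up.

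**Step 3: power after loss.** For each n, take the smallest number of cures r with P(X ≥ r | n, 0.672) ≤ 0.025. Power is P(X ≥ r | n, 0.7904). The normal approximation, with the null variance in the critical value, is shown alongside.

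| e | Treated with CIN2/3 | After 14% loss | r | Exact power | Normal approx. | HPV-positive needed for 140 |
|---|---|---|---|---|---|---|
| 0 | 140 | 120 | 92 | 77.6% | 82.3% | 400 |
| 5% | 133 | 114 | 87 | 79.9% | 80.1% | 422 |
| 10% | 126 | 108 | 83 | 75.5% | 77.7% | 445 |
| 20% | 112 | 96 | 74 | 73.0% | 72.2% | 500 |
| 30% | 98 | 84 | 66 | 60.4% | 65.7% | 572 |

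Exact power is slightly higher at 114 than at 120. This reflects the discreteness of the test: the attained level is 0.022 at 114 and 0.015 at 120. It is not a gain from having fewer women. The normal approximation shows the steady decline.

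**Step 4: the 400 are treated women.** Let f be the ineligible share of HPV-positive women and q the CIN2/3 proportion among them, with 35% overall. Then treated women with CIN2/3 = 400 × (0.35 − f·q) / (1 − f). Neither f nor q is in the documents.

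| f | q = 20% | q = 35% | q = 50% | q = 60% |
|---|---|---|---|---|
| 10% | 147 | 140 | 133 | 129 |
| 20% | 155 | 140 | 125 | 115 |
| 30% | 166 | 140 | 114 | 97 |

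On this reading the yield lies above or below 140 according to whether q is below or above 35%.

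**The case against.** The strongest reply is that nothing in section 3.3 is miscalculated. Both 140 and 120 reproduce, and what is missing is a stated planning assumption. That is right, and the point is put in those terms.

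A reader might go further and infer that 140 fails whichever 400 is meant, because women referred for large or endocervical lesions would carry more than their share of CIN2/3 and leave a prevalence below 35% among those treated. The documents do not support that. It needs CIN2/3 above 35% among referred women, which no section states. Women are also referred because the squamocolumnar junction is not fully seen, whatever their lesion, and they might have less CIN2/3. Sections 4.2 and 7.1 can be read as describing 400 treated women, and Step 4 shows that 140 could then be exceeded.

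Much larger shortfalls can be produced by assumption. With f = 30% and q = 60%, 400 HPV-positive women yield 400 × (0.35 − 0.18) = 68 treated with CIN2/3. That makes 72 of the 140 cases (51%) ineligible, and nothing in the documents supports so high a share.

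The 35% is cited to reference 24, which the reference list shows to be a paper on non-inferiority margins. This is probably a numbering slip: reference 23, a screening study among HIV-infected women in Kenya, is not cited in the text supplied. It calls for a corrected citation and is no evidence that 35% is too high. Whether the source counted only ablation-eligible women cannot be known from the documents.

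Nor does the plan conceal the population it treats. The criteria are set out openly, and section 1.3 calls eligibility for the two methods similar, so narrowing the hypothesis wording is secondary.

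**Conclusion.** The point holds as a gap in the sample-size justification. If the 400 are HPV-positive women, as sections 3.3 and 7.1 are worded, 140 and 120 are reached only when no woman with CIN2/3 is ineligible for ablation, while section 3.5.1 anticipates ineligible women. Any exclusion among women with CIN2/3 lowers the number; that direction does not depend on the assumed rate, but the size does. Across the assumed 5% to 30%, 133 to 98 women are treated and 114 to 84 remain after 14% loss. The loss of power is small at the low end and material at the high end: by the exact test, 60.4% at 84 women against 77.6% at 120.

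If the 400 are treated women, 140 is unsupported, because the 35% is stated for a wider group. It is not shown to be too high. The power figures assume the plan's boundary of 67.2%, its difference of 0.0184 and its one-sided 0.025.

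**What to change.** In section 3.3 and the synopsis:

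- State whether the 400 counts HPV-positive women or treated women.
- Apply a CIN2/3 proportion, with a correct citation, to HPV-positive women who meet the ablation criteria. If the source covers all HPV-positive women, say so and state the assumption that carries it over.
- Replace 140 and 120 with the expected number of treated women with CIN2/3, before and after loss, under a stated range of ineligibility.
- Restate the power at those numbers, using the exact test named in section 7.1.

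Reconcile section 7.1, which is worded as if all 400 HPV-positive women are treated, with the referral rule in sections 3.1 and 5.1.

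The cost is that the stated size and power become less favourable. The change is to text and calculation only and needs no extra patients or procedures. It does not restore 140; it makes the planned precision honest. If the sponsor wishes to keep 140 treated women with CIN2/3, the last column of the Step 3 table shows how many HPV-positive women that would take under each assumption.

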5.1 HPV Self-Testing

In this study, cervical cancer screening will be done using HPV testing via self-sampling.

HPV testing at baseline will be performed using patient self-collected samples. After providing informed consent, participants will be provided with visual and verbal instructions for HPV self-collection and offered a private area to perform self-collection before returning the kit to the health provider. During self-collection, women will be instructed to proceed to a designated private area with the collection brush and tube. While inside the collection area, she will undress from the waist down. She will then open the cap of the collection tube and lay both the tube and the cap aside on a flat surface. Next, they will open the case of the collecting brush, holding it from the plastic end that is the handle. She will then squat or stand in a comfortable position with her legs and thighs wide open. With one hand holding the plastic handle of the collection brush, she will use the other hand to open the outside of her vagina and gently insert the tip of the brush into her vagina. While holding the brush steady, she will gently advance the brush, with a slight left or right rotation for easy penetration until she feels resistance (at the cervix). At this point, she will turn the brush left or right five times to collect cells from the cervix. She will then remove the brush from her vagina and insert it into the collection tube until it reaches the bottom of the container. While holding the tube firmly with one hand, she will break off the handle of the brush with her other hand at the scored line against the mouth of the tube. She will then replace the lid of the collection tube and dispose of the brush handle in a rubbish container. A sanitizer for cleaning hands will be available for use before and after collection.

We will use the CareHPV™ system which tests for DNA of 14 high risk HPV types (16, 18, 31, 33, 35, 39, 45, 51, 52, 56, 58, 59, 66 and 68).²⁵ The self-collected samples will be placed in a cool area within the FACES laboratory and tests will be run in batches of 90, per the manufacturer's instructions, by a trained laboratory technician. Women who screen positive for HR-HPV will be offered a pelvic exam and treatment per the WHO recommendation.⁴ Visual inspection with acetic acid will be performed at the time of the pelvic exam to determine eligibility for thermal ablation based on the size of the lesion and other characteristics, as recommended by the WHO and Ministry of Health.⁴ A HPV-positive woman will be considered a candidate for thermal coagulation if the squamocolumnar junction is fully visualized, the cervical lesions takes up less than 75% of the cervix, there is no endocervical component of the lesion, and the lesion is not suspicious for cancer. Women who do not meet these criteria will be referred to a tertiary facility for appropriate care.

